General considerations: The analyses described below are of continuous outcome measures, primarily changes in function outcomes and gene expression and either continuous or categorical predictors. All analyses will be performed as general linear models. Potential confounders of each analysis will be outlined below and a 10% rule for evaluating confounders will be used, namely including a potential confounder if a 10% or greater change is seen in the main predictor effect. In all instances, outcome variables will be evaluated for violation of regression assumptions and transformation of these variables will be considered as a remedy if needed. Analyses will generally be performed with an intent-to-treat approach, with sensitivity analyses performed to assess the role of drop-outs on the results.

This grant examines a complex interplay of exercise regimens, gene expression and functional measures, resulting in a number of hypotheses that require testing. We are cognizant of the role of type I error in this and in interpreting results, focus will be placed on the overall results of these analyses and not on the results of individual tests. Thus, for example, significant relationships among gene expression outcomes and treatment categories as a whole will be considered as support for these hypotheses and isolated significant associations will not be unduly weighted in the interpretation of results.

Randomization will be generated using a SAS program based upon permuted random blocks of variable size to assure approximate balance over time and will be stratified by sex and statin use.

Validation of Study Measurements: At the start of the study, there will be two assessments of physical function battery. Intraclass correlations will be used to determine the relative repeatability of the various components of the battery. This information will be included in all manuscripts using these measures.

- *Aim 1. To assess differences in functional outcomes (peak VO₂, 1RM) relative to the training therapy:*
a) *Aerobic vs. Strength vs. Aerobic-Strength regimens will be compared to one another b) Inspiratory Training will be compared to Aerobic-Strength:* In this aim, we compare the combined aerobic-strength training regimen to the single-therapy regimens of aerobic training and strength training, as well as the inspiratory training regimen. These comparisons will be made with changes in the functional outcomes (peak VO₂, 1RM) from baseline as the continuous outcome measures in separate models and training regimen as the categorical predictor in a general linear model, with the following factors considered as potential confounder variables: age, sex, and comorbidities. To limit the type I error rate, only the pre-planned comparisons of the combined aerobic-strength training to the other regimens will be considered. In addition, secondary analyses will consider the following aerobic, strength and inspiratory variables as outcome variables in similar analyses to those outlined above: 6MWT, sit-to-stand, and hand grip strength.

- **Aim 2. To assess gene expression and skeletal muscle perfusion in relation to the different training regimens:** In this aim, we examine the change from baseline to post-exercise regimen in the expression of proteolytic (FoxO and Ubiquitin) and anti-proteolysis (IGF-1 and PGC-1 α) genes as predictors of the change in functional outcomes (peak VO₂, 1RM) over the same period. Separate general linear models for each functional outcome will be performed with gene expression changes as the primary predictor and the following variables considered as potential confounders: age, sex, and comorbidities. As above, a 10% rule for introducing confounding variables and the transformation of outcome variables to deal with regression assumption violations will be considered.

Treatment regimens will also be categorized as those with and without direct skeletal muscle stimulation and this categorical variable will be considered as a predictor of a change in the expression of proteolytic and anti-proteolysis genes in general linear models in a similar fashion to that described above. In addition, similar general linear models will be used with changes in skeletal muscle perfusion as a continuous outcome and aerobic and inspiratory training vs. strength-only training as a categorical predictor with similar potential confounders as noted above.

Secondary analyses will include assessment of the relative impact of changes in skeletal gene expression vs. changes in perfusion dynamics as predictors of changes in function and quality of life as outcomes. Measures of changes from baseline in serum inflammation, cytokines, and adipokines, and effects of muscle histology will be included as covariates in these analyses. General linear models will be used (outlined above).

Sample size/Power: In this study, we plan to recruit 210 individuals and assign them to one of 4 treatment arms, i.e., randomized between aerobic, aerobic strength, and IMT in VAPHS and between aerobic and inspiratory muscle training in Boston. Sample size calculations are based on 20% attrition over the course of the study. In general, a sample size of 40 per group, using a t-test of independent samples as a simplified model, results in an effect size of 0.64 SD units for 80% power, using a two-sided alpha of 5%.

- **Aim 1:** For this aim, we present calculations for detecting differences in peak VO₂. Previous work by Becker (108) shows a $2.1 \text{ mL O}_2 \cdot \text{kg}^{-1} \cdot \text{min}^{-1}$ change in peak VO₂ in a 6 month aerobic-strength training regimen. Similarly, Tyne-Lenne, et al. shows a $1.1 \text{ mL O}_2 \cdot \text{kg}^{-1} \cdot \text{min}^{-1}$ change in a strength-only regimen (109), HF-ACTION (85) shows a $0.6 \text{ mL O}_2 \cdot \text{kg}^{-1} \cdot \text{min}^{-1}$ change in an aerobic regimen and the IMT trial by Dall'Ago et al. (12) shows a $4 \text{ mL O}_2 \cdot \text{kg}^{-1} \cdot \text{min}^{-1}$ change with inspiratory training. Standard deviations [SD] of the change in peak VO₂ over an exercise regimen are not directly available but using interquartile range values from the largest study [HF-ACTION, n=1442], we obtain a SD value of 2.2 for a 3-month intervention. This would correspond to detecting a difference of $1.26 \text{ mL O}_2 \cdot \text{kg}^{-1} \cdot \text{min}^{-1}$ in any comparison with 80% power, assuming a SD=2.2.

- **Aim 2:** In a similar fashion, a simplified comparison of those with gene expression below the median vs. those above the median would be able to detect a difference of $1.26 \text{ mL O}_2 \cdot \text{kg}^{-1} \cdot \text{min}^{-1}$ in peak VO₂ with 80% power. Analyses of combined training groups facilitates capacity to detect smaller differences between groups.

Study Data Management and Quality Control: Prior to the initiation of the study, all investigators and research staff involved in clinical activities will meet to review study procedures and will complete all required trainings on data and patient privacy procedures. Documentation of any protocol breaches will be required. Each protocol violation will be evaluated by the principal investigator, and a determination made regarding the validity of any justification for the violation.

The clinical database with all research data will be stored on VA network drives and housed behind the VA firewall on VA owned and maintained servers, which are backed up on a regular schedule. All computers will have Kerberos passwords and come equipped with antivirus software. Data will not be stored on desktops or on non-VA servers. Study data will be coded with a unique study identifier for each participant and stored in a de-identified manner. A study data set without identifiable information will be used for all data analysis. Identifiable information will be collected for patient tracking and safety purposes, but will only be kept for as long as the study is active. De-identified clinical data will be stored separately from the participant's name, contact information, and real SSN. Access to the cross-walk file linking the participant's identifiers and their study data will be restricted to the project manager. This file will be destroyed according to CSP policy after the study ends. Study data will be retained and stored after the study ends according to federal and local VA regulations. Access to the study data is heavily restricted to individuals with approval from the principal investigator to access the data. Individuals must be properly credentialed research staff and must be compliant with VA security trainings (i.e., Research Data Security, HIPAA and VA Privacy Training, Cyber-Security, and Good Clinical Practices).

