[name] also spearheaded a related study comparing TC to aerobic training (AT) in a HF-PEF population. After 12 weeks of training, change in peak VO₂ was similar between groups, but 6MWT distance increased more after TC ($+69 \pm 46$ m vs. $+10 \pm 31$ m, $p=0.02$). Furthermore, while TC and AT were similar with respect to Minnesota Living with Heart Failure score and self-efficacy, POMS-depression scores improved more in TC (-1.7 ± 2.8 vs. $+1.6 \pm 3$, $p=0.05$). Cardiorespiratory parameters during training showed lower oxygen uptake ($4.3 \text{ mL O}_2 \cdot \text{kg}^{-1} \cdot \text{min}^{-1}$ vs. $9.4 \text{ mL O}_2 \cdot \text{kg}^{-1} \cdot \text{min}^{-1}$, $p<0.01$), respiratory rate and heart rate with TC relative to AT. Overall, the utility of TC to achieve similar or better performance benefits with a lower aerobic stimulus reinforces [name] contention that *skeletal muscle may be a key determinant of function*. TC may provide particular benefit with its focused skeletal muscle emphasis. That study is now submitted for publication.

Working with [name], [name] has also completed a series of analyses on CPX for HF patients. One project focused on chronotropic incompetence among systolic HF patients who were pacemaker-dependent for their exercise HR responses (88). Patients with pacemakers received higher doses of beta-blockers, had worse chronotropic incompetence (95 vs. 71%, $p=0.001$) and worse aerobic functional performance (12.2 ± 3.4 vs. $14.2 \pm 4.1 \text{ mL O}_2 \cdot \text{kg}^{-1} \cdot \text{min}^{-1}$; $p=0.004$); the study indicates that function could likely be improved if pacemaker settings were reevaluated.

In another analysis with Drs. [name] and [name] focused on differences in functional capacity in the time after a HF patient reached his/her VAT (89). Patients who ultimately stopped exercising due to leg fatigue demonstrated much greater capacity to exercise beyond their VAT than patients who stopped exercising due to dyspnea. *This study suggests that differences in the time after someone reaches the VAT may be an important consideration in HF management. It seems likely that differences in skeletal muscle may underlie these functional differences, such that primary focus on skeletal muscle may improve outcomes.*

3. Muscle proteolysis by the ubiquitin-proteasome system (UPS) in HF and regulatory role of IGF-1 demonstrated in an animal model

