	Visit 2 (within one week of visit 1)	Skeletal muscle biopsy; Serology and DXA scan Randomization
	Visit 3 (2-3 days after visit 2) (VABHS only)	Reassessment of biopsy site
Exercise Training	Visits 3/4-38/39	Exercise training sessions (3X/weekly; 60 minutes; 12 weeks)
Post assessment	Visit 39/40-41/43	Post-exercise assessment battery and additional group of assessments completed at visits 1 to 2/3

Table 5: Expansion to a Multi-Site Trial

	Recruitment goals	Exercise arms
VAMC Pittsburgh	100	Aerobic (35), Combined aerobic-strength (30 enrollees), IMT (35 enrollees)
VAMC Boston	50	Aerobic (25 enrollees); IMT (25 enrollees)

Total: 150 HF patients: Aerobic—60; IMT—60; Combined—30;

Study Population

• ***Study Population:*** 150 male and female systolic HF patients with mild-moderate symptoms while on optimal medical therapy will be enrolled. This target will allow for adequate power to address the study objectives even after accounting for a 20% drop-out rate due to attrition and/or suboptimal tissue samples for genetic analysis. Given the expansion to two campuses, and the variation in randomization at each site, the overall proportions of patients enrolled will vary from the original study design but still provide a sound statistical foundation for the anticipated analyses (see statistics section below).

• HF diagnosis will be contingent on a previous hospitalization for HF or physician assessment of HF associated. Each candidate will be examined at the time of enrollment by a cardiologist to ensure that he/she is clinically stable.

• ***Inclusion Criteria:***

- NYHA class II or III for the previous three months despite a minimum of 6 weeks of optimal treatment

- Age \geq 50 years

- Left ventricular EF (LVEF) (by echocardiogram or radionucleotide imaging study within 12 months of enrollment).

- Optimal therapy according to AHA/ACC and HFSA HF guidelines, including treatment with ACEI and beta-blocker therapy (for at least 6 weeks), or have documented reason for variation, including medication intolerance, contraindication, patient preference, or personal physician's judgment.

✓ Patients using aspirin (ASA) will be eligible, but asked to hold the medication for 48 hours prior to biopsy. This technique has previously been used with consistent safety. Patients will also be asked to avoid non-steroidal anti-inflammatory medications (NSAIDs) for 48 hours prior to the biopsy.

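### Aim 1 contrasts rest by default on one pooled variance, with the combined arm half the size of its comparators and transformation the only named remedy; arm-specific variances should be prespecified.

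*Combined protocol and SAP*

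**What the plan says.** The General considerations of the statistics section state: "All analyses will be performed as general linear models". On assumptions, they say that "outcome variables will be evaluated for violation of regression assumptions and transformation of these variables will be considered as a remedy if needed"; the Aim 2 text repeats this. The statistics section mentions no Welch-type contrast, robust standard error, arm-specific variance or rank method.

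For Aim 1 the outcomes are "changes in the functional outcomes (peak VO₂, 1RM) from baseline as the continuous outcome measures in separate models", with "training regimen as the categorical predictor in a general linear model". To limit type I error, only contrasts of combined aerobic-strength training with each other regimen count.

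Table 5 gives the allocation: "Total: 150 HF patients: Aerobic—60; IMT—60; Combined—30". It has no strength-only enrollees, so two Aim 1 contrasts can be run: combined vs aerobic and combined vs IMT.

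The Sample size/Power section says that SDs of change in peak VO₂ are not directly available. It takes one value from the interquartile range of a large aerobic training trial: "we obtain a SD value of 2.2 for a 3-month intervention". That section plans 210 patients in four arms and works with 40 per group. Overall Study Protocol and Study Population plan 150.

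**The concern.** With unequal arms, a pooled-variance contrast is valid only if the spread of change is similar in all arms. The larger arms dominate the pooled estimate, while the smallest arm contributes most to the true variance of the difference. If the combined arm is more variable than the others, p-values and confidence intervals are too optimistic; if less variable, too conservative. An arm outside the contrast also enters the pooled estimate and can distort it.

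The three regimens are different stimuli, and nothing in the documents shows that their changes have equal spread. If a check finds unequal spread, the only remedy named is to transform the outcome. That does not target unequal variance between arms, and it moves the result off the mL/kg/min scale on which the trial was planned. These contrasts are the trial's main functional comparisons.

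**Working it through.** **1. The plan's own figures.** For 40 vs 40, two-sided 5% and 80% power, the noncentral t gives a detectable effect of 0.634 SD, so the stated 0.64 reproduces. The stated 1.26 mL/kg/min does not follow from it: 0.64 × 2.2 = 1.41. The normal approximation gives 48 per group for 1.26 with SD 2.2. That equals 60 less 20% attrition, which is the size of the aerobic and IMT arms but not of the combined arm.

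**2. Inputs.**
- Enrolled 30/60/60 (Table 5), attrition 20% (Sample size/Power). Evaluable: combined 24, aerobic 48, IMT 48. Residual df = 120 − 3 = 117.
- SD ratio between arms: not in the documents, so assumed over a range.
- Normal data, no true mean difference, no covariates.

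**3. Formula, with a worked case.** Set the SD of the other two arms to 1 and that of the combined arm to r.
- Pooled variance = (23r² + 47 + 47)/117.
- Variance the model uses = pooled variance × (1/24 + 1/48).
- True variance = r²/24 + 1/48.

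At r = 1.5 the pooled variance is (51.75 + 94)/117 = 1.246. The model uses 1.246 × 0.0625 = 0.0779, and the true value is 0.09375 + 0.02083 = 0.1146. The standard error ratio is √(0.0779/0.1146) = 0.82.

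**4. Simulated type I error, nominal 5%, combined vs one other arm.**

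| Combined-to-other SD ratio | Pooled SE / true SE | Type I error, pooled |
|---|---|---|
| 0.67 | 1.19 | 2.0% |
| 0.8 | 1.11 | 3.1% |
| 1.0 | 1.00 | 5.0% |
| 1.25 | 0.90 | 7.8% |
| 1.5 | 0.82 | 10.5% |
| 2.0 | 0.73 | 15.4% |

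Welch stays at about 5% throughout, and HC3 standard errors at 4.9–5.2%.

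**5. Other patterns of spread.**
- Only the arm outside the contrast is more variable, by 1.5 or 2.0: 1.7% or 0.4%.
- Spread rises linearly with the mean changes in Sample size/Power (aerobic 0.6, combined 2.1, IMT 4). The combined SD is then 1 + (R − 1) × 1.5/3.4, where R is the assumed IMT-to-aerobic SD ratio:

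| R | Combined SD | Combined vs aerobic | Combined vs IMT |
|---|---|---|---|
| 1.5 | 1.22 | about 3% | about 6% |
| 2.0 | 1.44 | about 2% | 6.5% |
| 3.1 (assumed extreme) | 1.93 | about 1% | just under 7% |

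- Equal arms of 40, combined arm 1.5 or 2.0 times as variable: 6.8% or 8.0%.

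**6. Transformation.** With the plan's means, SD 2.2 and normality, the share of negative changes is Φ(−0.6/2.2) = 39% in the aerobic arm and Φ(−2.1/2.2) = 17% in the combined arm. Log, square root and Box-Cox of the raw change are undefined for those patients.

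**7. Cost of Welch if variances are equal.** Welch df = 0.0625² / [(1/24)²/23 + (1/48)²/47] = 46. The critical values are 2.013 vs 1.980, a ratio of 1.016. Power for 1.26 with SD 2.2 at 24 vs 48 is 61.0% against 62.1% pooled.

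**The case against.** The strongest reply is that the size of the problem depends on an SD ratio nobody knows. That is correct. A reader might infer from Preliminary Data, section 2, that arms with larger mean change have larger spread, and so that the planned intervals are too narrow. The tai chi comparison, where "6MWT distance increased more after TC", has ± values of 46 and 31 (ratio 1.48), and a resistance-training study has 8.8 against 2.8 for strength (ratio 3.1). The documents do not support that inference:
- The same resistance-training study reports 6MWT changes of +49 ± 14 m in trainers and −3 ± 19 m in controls, a ratio of 0.74 in the opposite direction.
- The tai chi study's depression score has 2.8 against 3, a ratio of 0.93.
- None of these is a combined-training contrast on peak VO₂ in systolic HF. The strength figures compare trainers with controls, whereas every arm here trains. The ± values are not labelled as SD or SE.

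Even if spread did follow mean change, IMT, a large arm, would be the most variable. Step 5 then shows one conservative contrast and one only mildly liberal.

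It is also fair that the plan promises assumption checks, says only that transformation will be considered, and never states a pooled variance outright; that is the model's default. Nor is transformation impossible: log of post over baseline is defined, as peak VO₂ and 1RM are positive, and shifted or signed transforms exist. What remains is that none of these is chosen to equalise arm variances, all leave the planning scale, and no method for unequal variance is named.

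**Conclusion.** The point holds as a weakness in specification that is cheap to repair. It does not show that the planned intervals will be wrong. The distortion is modest for combined-to-other SD ratios between about 0.8 and 1.25 (roughly 3% to 8%) and serious from about 1.5 (10.5%, and about 15% at 2.0). It is conservative if the combined arm is less variable or the arm outside the contrast is more variable. The direction cannot be known in advance.

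These figures assume 24/48/48 evaluable, normal data and no covariates. They depend heavily on the 2:1 imbalance: with 40 per group the error at ratio 1.5 is 6.8%. The conflicts between 150 and 210 patients, and between 40 per group and 60/60/30, therefore decide how much this matters. A reader might extend the point to every comparison in the plan. It covers only the two Aim 1 contrasts that have enrollees: combined vs strength-only has none in Table 5, and Aim 2 regroups the arms.

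**What to change.** In General considerations and Aim 1, for the functional change scores, replace transformation as the remedy for unequal variance. State that each planned contrast is analysed on the original scale with arm-specific variances: a Welch contrast, or HC3 standard errors in the covariate-adjusted model. Make this the prespecified analysis rather than one triggered by a variance check. The transformation sentence can stay for other outcomes such as gene expression.

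Reconcile the total, the number of arms and the per-group size across Overall Study Protocol, Table 5, Sample size/Power and Limitations, and restate the detectable difference for the combined arm's actual size.

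An ordinary permutation test of the mean difference is not a safeguard: at 24 vs 48 it gave 8.4% and 10.8% type I error at SD ratios 1.5 and 2.0. If a permutation test is wanted as a sensitivity analysis, it should be studentized.

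The cost is a sentence or two in the plan. If variances are equal, intervals are about 1.6% wider and power falls by about one point.

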An implicit aspect of this work is that it attests to the first-class research infrastructure we have been able to organize in the last 3 years. We have developed a highly successful program and research facility at the VA Boston Healthcare System (VABHS), facilitating recruitment, functional assessments, muscle biopsies, dual-emission X-ray absorptiometry (DXA), exercise training, and echocardiography, as well as tissue storage, data storage, and data analysis. We have become a substantial resource within the VABHS research program, growing our own program and work, but also enriching other investigators whose work entails exercise assessment, exercise training, and exercise science.

- *Phase I:* We compared functional capacity between HF and controls, evaluating CPX indices, strength testing, body composition, and basic clinical measures. We showed that key aerobic and strength indices were significantly decreased in HF patients (peak VO_2 [15.4±4.2 vs. 23.4±6.6, $\text{mLO}_2\cdot\text{kg}^{-1}\cdot\text{min}^{-1}$ p<0.0001], VAT [10.9±2.1 vs. 14.4±4.0 $\text{mLO}_2\cdot\text{kg}^{-1}\cdot\text{min}^{-1}$, p<0.0001], VE/V CO_2 slope [35.7±10.6 vs. 29.1±4.6, p<0.0001], 1RM [154.8±52.0 vs. 195.3±56.8kg, p<0.01], power [226.4±99.2 vs. 313.3±130.6 watts, p<0.01]), and the 6MWT distance (388.8±114.9 vs. 536.5±182.7 meters, p<0.001) reflecting the pathophysiological-associated functional decrements in an HF population.

Table 1

Phase I. Evolving scientific insights regarding functional measures and body composition, in HF vs. controls.

Title	Summary	Venue
Comparing physical and functional measures in HF patients and healthy controls	While age correlated inversely to all functional variables in HF and controls, differences between groups were evident in relation to peak VO_2 , leg endurance, 6MWT, and the Duke Activity Status Index (DASI). While Peak VO_2 correlated with leg endurance, DASI did not correlate with physical function measures.	American College of Sports Medicine, 2011
The Influence of Functional Parameters on Quality of Life in Systolic HF Patients	The Kansas City Cardiomyopathy Questionnaire (KCCQ) correlated with aerobic indices in HF patients but not strength parameters. Aerobic capacity may be a key determinant in quality of life in HF patients.	Society of Behavioral Medicine, 2011

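### The Aim 1 models analyse change in function without the baseline value of the outcome, giving up a modest amount of precision that the collected data would supply

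*Combined protocol and SAP*

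**What the plan says.** All references are to the combined protocol and SAP.

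- **Aim 1 (statistics section).** The outcomes are "changes in the functional outcomes (peak VO₂, 1RM) from baseline as the continuous outcome measures", with one general linear model per outcome and regimen as the categorical predictor. The model is specified "with the following factors considered as potential confounder variables: age, sex, and comorbidities". Secondary functional outcomes (6MWT, sit-to-stand, hand grip) are analysed in a similar way. Only comparisons of the combined arm with the other regimens are pre-planned.
- **General considerations.** Confounders are to be set out analysis by analysis, and the entry rule is "including a potential confounder if a 10% or greater change is seen in the main predictor effect". Randomization is stratified by sex and statin use.
- **Aim 2.** Regimens are grouped by whether they stimulate skeletal muscle directly, and "this categorical variable will be considered as a predictor of a change in the expression of proteolytic and anti-proteolysis genes".
- **Sample size/Power.** The calculation takes "a sample size of 40 per group, using a t-test of independent samples as a simplified model", and this "results in an effect size of 0.64 SD units for 80% power, using a two-sided alpha of 5" per cent. For the change in peak VO₂, "we obtain a SD value of 2.2 for a 3-month intervention". Attrition is put at 20%.
- **Preliminary Data, Phase I.** Pilot peak VO₂, heart failure versus controls, is "15.4±4.2 vs. 23.4±6.6".

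The baseline value of the outcome is not named as a covariate in any of these places, nor in the broader list under Effects of Confounders.

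**The concern.** A change score fixes the coefficient of baseline at one. When the true slope of follow-up on baseline is below one, the change is negatively related to baseline, and part of its variance could have been removed by putting baseline in the model. The data are already in hand, so nothing is saved by leaving it out.

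The 10% rule does not repair this. Baseline is not a named candidate, and the rule selects on movement of the regimen effect, whereas a strong predictor of outcome that is well balanced between arms improves precision without moving the effect.

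Two things are at stake. Every pre-planned Aim 1 contrast involves the combined arm, the smallest arm in Table 5, so precision is short. And nothing in the randomization balances baseline function, so a chance difference between arms carries partly into the estimate.

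**Working it through.** **Inputs**
- SD of change in peak VO₂: 2.2 (Sample size/Power).
- Baseline SD: 4.2 (pilot heart failure group).
- Difference: 1.26 mL/kg/min (Sample size/Power).
- Arms: aerobic 60, IMT 60, combined 30 (Table 5). Less 20%: 48, 48 and 24.
- Assumption: equal SD at both visits. The documents give no follow-up SD and no pre-post correlation.

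**The plan's own figure.** With 40 per group, two-sided 5% and 80% power, the detectable effect is 0.634 SD by the t-test (0.626 by the normal approximation). Power at 0.64 SD is 80.7%, so the stated 0.64 reproduces. The companion figure of 1.26 at SD 2.2 does not follow from 40 per group, where 0.64 × 2.2 = 1.41. It matches 48 per group: (1.96 + 0.84) × 2.2 × √(2/48) = 1.26.

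**Implied correlation.** With equal SDs, var(change) = 2 × SD² × (1 − r), so
r = 1 − 2.2² / (2 × 4.2²) = 1 − 4.84/35.28 = 0.863.

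**Precision.** Ratio of baseline-adjusted to change-score error variance:
(1 + r)/2 = 1.863/2 = 0.931, about 7% lower. Residual SD: 2.2 × √0.931 = 2.12.
This is worth 1/0.931 = 1.07, or about 7% more patients.

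**Power, 24 versus 48, difference 1.26.** √(1/24 + 1/48) = 0.25.
- Change score: noncentrality 1.26/(2.2 × 0.25) = 2.29, power 61.8%.
- Baseline included: 1.26/(2.12 × 0.25) = 2.38, power 64.8%.

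**Sensitivity to the equal-SD assumption** (baseline SD 4.2 and change SD 2.2 held). The covariance is c = (s² + 4.2² − 2.2²)/2 for follow-up SD s, and the residual variance is s² − c²/4.2².

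| Follow-up SD | Slope of change on baseline | Variance gain |
|---|---|---|
| 3.5 | −0.29 | 31% |
| 4.2 | −0.14 | 7% |
| 4.5 | −0.06 | 1.5% |
| 4.74 | 0 | nil |
| 5.0 | +0.07 | 2% |

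The gain is never negative, apart from the one degree of freedom. For 1RM the documents give no change SD or correlation, so no figure can be stated.

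**Chance imbalance.** The SE of the baseline difference, 24 versus 48, is 4.2 × 0.25 = 1.05. A 2-SE imbalance is 2.1 mL/kg/min. The error in the change-score contrast, given that imbalance, is (1 − r) × 2.1 = 0.137 × 2.1 = 0.29, and 0.29/1.26 = 23%.

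A simulation of 20,000 null trials with complete data (24 versus 48) agrees:
- Over all randomizations, the mean error is 0.007 for change and 0.006 with baseline included; type I error is 5.1% and 4.9%; the variance ratio is 0.935.
- Given an imbalance of roughly two SE (1.5 to 2.5), the mean error is about 0.27 to 0.28 in size for change and 0.00 to 0.02 with baseline included; type I error is 7% to 8% against 5.1%.

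**Gene expression.** The rtPCR paragraph plans assays batched by exercise arm. Suppose a patient's two samples share a batch (my reading; not stated outright) and the batch adds a constant of 0.5 SD (assumed). The constant cancels in the change score. With baseline as covariate, a fraction (1 − r) stays in the arm contrast: 0.5 × 0.7 = 0.35 SD at an assumed r of 0.3, and 0.5 × 0.3 = 0.15 SD at r = 0.7. Simulating 48 (IMT) versus 72 (aerobic plus combined) with no true effect gives false-positive rates of about 46% at r = 0.3 and 19% at r = 0.7, against about 5% for the change score.

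**The case against.** **The change score is a valid analysis.** A reader might infer from the missing baseline term that the Aim 1 estimates are biased. They are not: under randomization the change score is unbiased on average and holds its type I error. The 0.29 is the error given a 2-SE imbalance, an event of roughly 5% probability. This objection stands, and the point is one of efficiency and of conditional error.

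**The gain is small and rests on mixed sources.** The 4.2 is from the pilot and the 2.2 is back-calculated from another trial's interquartile range. The 7% needs equal SDs, and it vanishes near a follow-up SD of 4.74. The contrast remains underpowered either way. This also stands. It limits the size of the point, but including baseline costs almost nothing even where the gain is nil.

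**The covariate list may be open.** Effects of Confounders adds height, weight, medications and other clinical parameters, so one cannot say that baseline could never enter. Even so, it is not named, and the 10% rule would not add it for precision.

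**Arm imbalance here is not only chance.** Boston randomizes to aerobic or IMT only, so about 20 of each 48 comparators (25 × 0.8) come from a site without the combined arm. A reader might suppose that baseline adjustment deals with this. It does not replace a site term. Within Pittsburgh the comparison is about 24 versus 28, where power at 1.26 goes from 52% to 55%.

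**The same fix looks natural for Aim 2.** The regimen-to-gene model has the same form, and it is tempting to ask for baseline expression there too. With assays batched by arm that could introduce error that the change score avoids, so the documents do not support the extension.

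**Conclusion.** The point holds for Aim 1 as a modest, nearly free improvement. At the documents' own SDs, and assuming equal SDs before and after training, including baseline lowers peak VO₂ error variance by about 7% and raises power for the combined-arm contrasts from about 62% to 65%. With baseline SD 4.2 and change SD 2.2 held, the gain runs from 31% at a follow-up SD of 3.5 to nil near 4.74. It cannot be quantified for 1RM. The second benefit is protection against an unlucky allocation: a 2-SE imbalance would otherwise move the contrast by about 0.29, or 23% of 1.26.

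These figures use the Table 5 arm sizes less 20%; the sample-size paragraph's total of 210 does not match the 150 in that table. The conclusion does not depend on which total is right.

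**What to change.** In the statistics section, Aim 1, state that each model for peak VO₂, 1RM and the secondary functional outcomes always includes the baseline value of that outcome as a covariate, outside the 10% rule. Report the baseline-adjusted regimen difference as the main result and the unadjusted change as a sensitivity analysis. Fixing this in advance also removes any choice between the two after the baseline table has been seen.

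The cost is one sentence and one degree of freedom per model; the baseline values are already collected.

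Handle site separately, because the combined arm exists only in Pittsburgh. Leave the Aim 2 regimen-to-gene model on the change scale while rtPCR is batched by exercise arm.
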